## 8.1 Part 1: Interim Safety Analysis

**Cut-off for analysis:** 20 enrolled subjects from each of the cohorts C1 to C6 with acute (24-hours post-dose) safety data.

Responsible party: PPD

A safety (acute AE only) analysis is planned in Part 1 after 20 subjects from each of the treatment arms C1 to C6 are treated. The acute (24 hour) safety data of all six treatment arms will be summarized per each treatment arm and the descriptive output evaluated by the SMC, to decide the inclusion of the 7th arm (C7). Output to be included in the SMC data report is detailed in Appendix C of the SMC charter (SMC Decision 1).

No adjustment for multiplicity will be made for any safety analyses. Analysis results will be shared with the SMC prior to the first scheduled SMC meeting.

## 8.2 Part 1: Final Analysis

Cut-off for analysis: Data for all subjects in Part 1 is available.

Responsible parties: PPD , Merck KGaA.

At the end of Part 1, the final analysis of Part 1 will be conducted on clean safety and efficacy data. The SMC will assess the data (SMC Decision 2 and 3; safety and efficacy) to recommend an optimal ODT dose (L-PZQ or rac-PZQ) for Part 2.

Due to technical challenges in the preparation of the PK samples, PK analysis may be abandoned, in which case the data will only be listed.

All primary, secondary endpoints and safety endpoints will be analysed. No adjustment for multiplicity will be made. Analysis results will be shared with the SMC prior to the next scheduled SMC meeting.

## 8.3 Part 2: Interim Safety/Efficacy Analysis

Cut-off for analysis: 10 subjects in Part 2 with complete safety and efficacy data.

Responsible parties: PPD

, Merck KGaA.

Part 2 of the study will also include a SMC interim safety analysis. After 5 to 10 infants of 13 to 24 months have been enrolled, the overall safety and efficacy data in these children will be evaluated by the SMC for the decision to include the lower age group (cohort C9). Due to the low number of subjects and the expected high variability in the PK, the PK data from these infants are not mandatory for the decision to include C9. SMC will also decide whether dose level adaptations are needed before starting to enrol C9.

All primary, secondary endpoints and safety endpoints will be analysed. The small sample size of this part of the trial limits the applicability of inferential statistics. For this reason and the exploratory nature of this part of the trial, no adjustment for multiplicity will be made. Analysis results will be shared with the SMC prior to the next scheduled SMC meeting. Output to be included in the SMC data report is detailed in Appendix C of the SMC charter (SMC Decision 4).

## 8.4 Final Analysis of Trial Data

Cut-off for analysis: Final database lock.

Responsible parties: PPD , Merck KGaA.

Following completion of Part 2 of the trial, the final trial analyses identified in this SAP will be performed only after the last subject has completed the treatment phase of the trial with all trial data in-house, all data queries resolved, and the database locked. A data review meeting will be held prior to database lock. In addition, no database can be locked until this SAP has been approved.

All primary, secondary endpoints and safety endpoints will be analysed. The small sample size of this part of the trial limits the applicability of inferential statistics. For this reason and the exploratory nature of this part of the trial, no adjustment for multiplicity will be made.

## 9 Changes to the Planned Analyses in the Clinical Trial Protocol

The statistical methods as described in the protocol were adopted.

## 10 Protocol Deviations and Analysis Sets

## **10.1** Definition of Protocol Deviations and Analysis Sets

Important protocol deviations are protocol deviations that might significantly affect the completeness, accuracy, and/or reliability of the study data or that might significantly affect a subject's rights, safety, or well-being.

Important protocol deviations include:

- Subjects that are dosed on the study despite not satisfying the eligibility criteria, i.e. any inclusion/exclusion criteria violations
- Subjects that develop withdrawal criteria whilst on the study, but are not withdrawn
- Subjects that receive the incorrect treatment or an incorrect dose
- Deviation from GCP.

The following deviations will be identified and confirmed prior to or at the Data Review Meeting at the latest.

- Important protocol deviations include:
  - Subjects that receive any prohibited medications/foods/fluids as outlined in sections 5.3.1, 5.3.2, 6.5.2 and 6.5.3 of the protocol (see Appendix B for further guidance);
  - Any missed doses of Investigational Medicinal Product (IMP)
  - Vomiting within the first hour of IMP administration
  - Any medical condition that may modify the pharmacokinetic profile of the IMP or compromise the natural immunity of the subject

- Stool and urine samples required for assessing the any of the study endpoint are missing or collected out-of-window
- Subset(s) of these important protocol deviations are clinically important, if leading to the exclusion of a subject from an analysis set (see section 10.2)

Important protocol deviations should be documented in the SDTM DV dataset whether identified through sites monitoring, medical review or programming. Important protocol deviations will be identified by programming and all clinically-important protocol deviations need to be in listings and described in an appendix of the CSR.

## **10.2** Definition of Analysis Sets and Subgroups

### Screening Analysis Set (SCR)

The screening analysis set includes all subjects who signed the informed consent.

### **Modified Intention-to-Treat Set (mITT)**

Modified intention-to-treat (mITT) population or analysis set includes all randomized subjects who have baseline measurement. In both parts 1 and 2, children who require malaria treatment following IMP administration will not be included in the mITT analysis set.

### Safety Analysis Set (SAF)

Safety analysis set includes all subjects who have received at least one dose of treatment.

#### Per Protocol Analysis Set (PP)

Per-protocol analysis set includes all subjects that constitute the mITT population with at least one post-baseline measurement and no clinically-important protocol deviations, including:

- Inclusion/exclusion violations
- Subjects that develop withdrawal criteria whilst on the study, but are not withdrawn
- Subjects that receive the incorrect treatment
- Subjects that receive any prohibited medications/foods/fluids as outlined in sections 5.3, 6.5.2 and 6.5.3 of the protocol;
- Any missed doses of IMP
- Any medical condition that may modify the pharmacokinetic profile of the IMP or compromise the natural immunity of the subject
- End-of-study stool (C1-C9) samples required for assessing the primary endpoint are missing or collected out-of-window (as described in section 11 of this SAP)

### **PK Analysis**

Due to technical challenges in the preparation of the PK samples, PK analysis may be abandoned, in which case the data will only be listed.

## 10.2.1 Subgroup definition and parameterization

Subgroup analyses will be performed on subgroups as defined below.

The final parameterization will be updated and fixed at the Data Review Meeting at the latest and documented in an amendment to this SAP if different from the following definition.

The following subgroups will be defined:

- Age (some age ranges may not be applicable, depending on certain trial adaptations) Part 1:
  - 2 years  $\leq$  age < 4 years
  - 4 years ≤ age ≤ 6 years (Ref) Part 2:
  - 3 months  $\leq$  age < 13 months
  - 13 months  $\leq$  age < 24 months (Ref)
- Gender
  - Male (Ref)
  - Female
- Severity of infection (as assessed at Pre-screening [D-28 to D-1])
  - S. mansoni infection
    - Light infection: 1 99 eggs per gram of faeces (Ref)
    - $\circ$  Moderate/heavy infection:  $\geq 100$  eggs per gram of feaces
- Treatment group
  - Biltricide® 3x20mg/kg t.i.d
  - Biltricide® 40mg/kg single dose (Ref)
  - rac-PZQ ODT 1x40mg/kg single dose
  - rac-PZQ ODT 1x60mg/kg single dose
  - L-PZQ ODT 1x30mg/kg single dose
  - L-PZQ ODT 1x45mg/kg single dose
  - L-PZQ ODT 1x60mg/kg single dose
- Trial center/country
  - PPD
  - PPD

## 11 General Specifications for Statistical Analyses

All analyses will be performed using SAS® Software version 9.1 or higher. Unless otherwise indicated all analyses will be presented by treatment group.

### Data handling after cut-off date:

Data other than the date of death and the date last known to be alive obtained after the cut-off will not be displayed in any listings or used for summary statistics, e.g. laboratory values of samples taken after data cut-off, AEs with onset date after data cut-off, etc. will not be included in any analysis or listing.

#### Significance level:

All statistical tests mentioned in this SAP are to be regarded as exploratory. All statistical tests comparing treatment arms will be performed two-sided. If confidence intervals are to be calculated, these will be two-sided with a confidence probability of 95%, unless otherwise specified in this SAP.

#### Presentation of continuous and qualitative variables:

Continuous variables will be summarized using the following descriptive statistics, i.e.

- number of subjects (N), number of subjects with non-missing values
- mean, standard deviation
- median, 25th Percentile 75th Percentile (Q1-Q3),
- minimum, and maximum,

Qualitative variables will be summarized by frequency counts and percentages.

Unless otherwise stated the calculation of proportions will be based on the number of subjects of the analysis set of interest. Therefore counts of missing observations will be included in the denominator and presented as a separate category.

In case the analysis refers only to certain visits percentages will be based on the number of subjects still present in the trial at that visit, unless otherwise specified.

Statistic	Reporting convention	
Mean	Observed + 1 decimal place	
SD, SEM	Observed + 2 decimal place	
Minimum	Observed	
Median	Observed + 1 decimal place	
Maximum	Observed	
CV%	Up to 1 decimal place	
Point Estimate	Observed + 1 decimal place	

The following conventions are applied for reporting descriptive statistics of all continuous:

95% CI

Observed + 1 decimal place

#### **Definition of baseline:**

In general, the last non-missing measurement prior to first IMP administration will serve as the baseline measurement.

#### **Definition of pre-treatment value:**

N/A.

#### **Definition of duration:**

If required, duration will be calculated by the difference of start and stop date + 1 (if not otherwise specified).

The time since an event will be calculated as reference date minus date of event

#### **Conversion factors:**

The following conversion factors will be used to convert days into months or years: 1 month = 30.4375 days, 1 year = 365.25 days.

#### **Study windows:**

Visit	Activity	Trial day	Window period
Visit 1	Pre-screening	Day -28 to Day -1	-28 to -1
Visit 2	Screening / Randomisation / IMP administration / Treatment period	Day 1	1
Visit 3	End of confinement	Day 2	2
Visit 4	Follow-up	Day 3	3+1
Visit 5	Follow-up	Day 8	8
Visit 6	End of study	Day 14 to Day 21	14 to 21 +3

#### Handling of missing data:

Unless otherwise specified, missing data will not be replaced.

In all subject data listing, imputed values will be presented. In all listings, imputed information will be flagged.

Missing statistics, e.g. when they cannot be calculated, should be presented as "nd". For example, if n=1, the measure of variability (SD) cannot be computed and should be presented as "nd".

Where tables are presented over time, the total of missing and non-missing observations at each time-point should reflect the population still in the trial at that time. This does not apply when imputations are made beyond trial withdrawal. For example, if a subject is still in the trial at the time-point but with missing data, it should be counted in the number of missing observations.

Trial day / Treatment day are defined relative to the date of start of treatment. Trial day 1 defines the day of randomisation, the day before is defined as Trial day -1 (no Trial day 0 is defined). Treatment day will be calculated accordingly, i.e. treatment day 1 is defined as the date of first administration of IMP to any one of the study cohorts, C1-C9. Treatment duration will be one day only.

If required for an analysis, incomplete date or date/time fields will be imputed as follows:

- Missing start dates will default to the first day of the month and first month of the year, if month is missing, subject to the following exceptions:
  - If and AE/concomitant medication/procedure start date is missing and month is the same as the month of IMP administration, then the start date will default to the IMP start date. If the month is different, the start date will default to the first day of the month.
  - If start date and month is missing and stop date is not before first IMP administration, then the start date will default to the IMP start date.
  - If start date and month and stop date is missing, then the start date will default to the IMP start date.
  - Missing start dates for medical history and medications stopped prior to IMP administration will not be imputed.
- Missing stop dates will default to the last day of the month and last month of the year, if month is missing, subject to the following exceptions:
  - If stop date is missing for a known medical history/previous medication, then the stop date will default to the IMP start date 1 day.
  - If stop date and month is missing for a known medical history/prior medication, then the stop date will default to the IMP start date 1 day.
  - If the stop date and month for a concomitant medication or AE is missing, it will default to the day of last contact with the participant.
- Unknown times will default to 00:00, subject to the following:
  - If an AE/concomitant medication/procedure start time is missing and day and month is the same as the date of IMP administration, then the start time will default to the IMP start time. If the day or month is different, the start time will default to 00:00.
  - If start time, date and month is missing and stop date is not before first IMP administration, then the start date/time will default to the IMP start date/time.
  - If start time, date and month and stop date is missing, then the start date/time will default to the IMP start date/time.
  - Missing start dates for medical history and medications stopped prior to IMP administration will not be imputed.
- Missing years will not be imputed.

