5.3.2 Exclusion Criteria

Subjects are not eligible for this study if they fulfil one or more of the following exclusion criteria:

- Treatment in the 4 weeks prior to study screening with PZQ, other anti-helminthic, anti-malarial or anti-retroviral compounds or any other medication that might affect the PK of PZQ such as certain antiepileptics (e.g., carbamazepine or phenytoin), glucocorticosteroids (e.g., dexamethasone), chloroquine, rifampicin or cimetidine (see Section 6.5.2 and Biltricide® SPC)For children being breast fed, treatment of the mothers/wet nurses with PZQ in the 3 days prior to administration of IMP
- Previous history of adverse reactions associated with PZQ treatment
- History of acute or severe chronic disease, including hepato-splenic schistosomiasis
- Marked increases of the liver transaminases (alanine aminotransferase and/or aspartate aminotransferase) above 3x ULN
- Fever defined as temperature above 38.0°C
- Debilitating illnesses such as tuberculosis, malnutrition, etc. as well as a medical history of seizures
- Mixed S. haematobium and S. mansoni infections
- Findings in the clinical examination of schistosome-infected children participating in the study as performed by the study clinician on the treatment day, that in the opinion of the

Investigator constitutes a risk or a contraindication for the participation of the subject in the study or that could interfere with the study objectives, conduct or evaluation

• Unlikelihood to comply with the protocol requirements, instructions and trial-related restrictions, e.g., uncooperative attitude, inability to return for follow-up visits, and improbability of completing the trial

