7.2 Demographic and Other Baseline Characteristics

At screening, the following demographic data will be collected: date of birth, date of informed consent signature, gender and height.

Medical history within the last year, consisting of all previous diseases as considered relevant by the Investigator and all hospital stays, will be recorded.

Previous medication consisting of all previous medications within the last 6 months as considered relevant by the Investigator and all regularly taken medications within the last 6 months will be recorded.

Use of caffeine or xanthine-containing beverages and concomitant medication will be assessed at screening.

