## 14 Previous, Concomitant and Prohibited Medications/Procedures

**Previous medications** are medications, other than trial medications and pre-medications for trial drug, which are taken within four weeks prior to first IMP administration and if the end date of the medication < date of "study day 1".

Previous treatment will be summarized from the "Concomitant Medications" eCRF page. Anatomical Therapeutic Chemical (ATC) term 2nd level and preferred term will be tabulated as given from the WHO Drug Dictionary March 2016 version. In case multiple ATC's are assigned to a drug, all ATC-2nd level will be used for reporting.

**Concomitant treatments** are medications, other than trial medications, which are taken by subjects any time on-trial (the end date of the medication  $\geq$  date of "study day 1", or medication that is ongoing with a start date  $\geq$  date of "study day 1").

Concomitant treatment will be summarized from the "Concomitant Medications" eCRF. ATC-2nd level and preferred term will be tabulated as given from the WHO Drug Dictionary current version. In case multiple ATC's are assigned to a drug, all ATC-2nd level will be used for reporting.

**Prohibited medications** are medications, other than trial medications, listed in section 6.5.2 of the trial protocol that are taken by subjects at any time.

- Prohibited prior medications will be summarized from the "Prior Drug History" eCRF page. ATC level 2 and preferred term will be tabulated as given from the WHO Drug Dictionary version of March 2016. In case multiple ATC's are assigned to a drug, all ATC-2nd level will be used for reporting.
- Prohibited concomitant medications, which includes medications that were started prior to dosing but were not stopped prior to dosing, will be summarised and listed separately. Prohibited concomitant medications will be identified from the "Concomitant Medications" eCRF page, using Appendix B as guide. ATC level 2 and preferred term will be tabulated as given from the WHO Drug Dictionary version of March 2016. In case multiple ATC's are assigned to a drug, all ATC-2nd level will be used for reporting.

All **Concomitant Procedures**, which were undertaken any time on trial, will be summarized according to the eCRF page "Concomitant Procedure".

- Concurrent procedures will be listed by verbatim term.

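### SAP section 11 overwrites a recorded stop month for previous medication with the day before dosing, and dates some adverse events at dosing without checking when they ended

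*SAP*

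**What the plan says.** SAP section 11 (Handling of missing data) starts from a reasonable default for stop dates: "Missing stop dates will default to the last day of the month and last month of the year, if month is missing". It then lists exceptions. The first is "If stop date is missing for a known medical history/previous medication, then the stop date will default to the IMP start date", followed by a one-day offset; the second begins "If stop date and month is missing for a known medical history/prior medication" and ends in the same default. In both, a minus sign before the final words appears to have been lost when the PDF was read, so I take the value as IMP start minus 1 day.

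SAP section 14 defines previous medications as those "which are taken within four weeks prior to first IMP administration" that ended before study day 1. Protocol 7.2 collects over a longer period: "Previous medication consisting of all previous medications within the last 6 months", where the investigator considers them relevant. Protocol 5.3.2 excludes "Treatment in the 4 weeks prior to study screening with PZQ, other anti-helminthic, anti-malarial" and other listed drugs, counting back from screening and not from dosing.

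For start dates, section 11 says that if the day of an adverse event, concomitant medication or procedure is "missing and month is the same as the month of IMP administration, then the start date will default to the IMP start date". The condition that the stop date must not precede dosing appears only in the next exception, for a missing day and month. A further bullet leaves start dates unimputed for medical history and for medications stopped before dosing. Adverse events are not named in it.

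**The concern.** An imputation rule should fill in what is unknown and keep what is known. The first stop-date exception does the opposite: a drug recorded as stopped months ago is re-dated to the day before dosing. In this trial, drug timing bears on eligibility (praziquantel, other anthelminthics, antimalarials), on the previous-medication table and, through SAP section 10.2, on the per-protocol set.

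The start-date rule has a similar fault for adverse events. An event that began and resolved before dosing in the same calendar month, with its start day missing, receives an onset later than its own end. SAP section 17.1 classifies events as treatment-emergent from their onset relative to first dosing, so the imputed date can move a pre-dose event into the safety tables.

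**Working it through.** The documents give no figure that depends on these rules, so there is nothing of the plan's own to reproduce. The check is to read the exceptions side by side and then apply them to dates.

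**Which case the first exception covers.** The second exception handles day and month both missing. If the first also meant that, it would be redundant. The start-date bullets use the same language, pairing a missing date with a known month, so date there means day. The first exception therefore governs a known month with a missing day.

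**One record.** Dosing 15 September 2017, stop recorded as May 2017, day unknown.
- SAP default, last day of the month: 31 May 2017, 107 days before dosing.
- SAP exception, dosing minus 1: 14 September 2017, 1 day before dosing.
- Capped rule, the earlier of last day of month and dosing minus 1: 31 May 2017.

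**Why an exception is needed at all.** If the stop month is the dosing month, the default gives a date on or after dosing for every dosing day. For a September stop in this example it gives 30 September, 15 days after dosing. A cap deals with this without discarding earlier months.

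**All dosing dates.** Assumptions: dosing on each of the 579 days from June 2016 to December 2017 (the Part 1 period); a known stop month 0 to 6 calendar months before the dosing month; screening 0, 7 or 28 days before dosing. A record counts as inside the window if its imputed stop is on or after screening minus 28 days.

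| Stop month before dosing month | Exception as written | Capped, screening on dosing day | Capped, 7 days before | Capped, 28 days before |
|---|---|---|---|---|
| 0 | 100% | 100% | 100% | 100% |
| 1 | 100% | 91.9% | 100% | 100% |
| 2 | 100% | 0% | 14.9% | 83.8% |
| 3 to 6 | 100% | 0% | 0% | 0% |

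The exception puts every record inside the window or later. For stops 3 to 6 months back, the recorded month rules that out under every screening offset. With screening on the dosing day, the window coincides with the four weeks before dosing used in SAP section 14. There the written rule admits every record 2 to 6 months back, and the recorded month admits none.

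**Where the wrong date goes.** The previous-medication table is affected directly, because a stop at dosing minus 1 always meets the section 14 definition. The split between previous and concomitant use is not affected, since dosing minus 1 is still before day 1. For medical history, SAP section 13.2 counts conditions without using dates, so only the derived dates are wrong.

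**Adverse events.** Take an infant screened on 8 May 2018 and dosed on 15 May. An event has its start recorded as May 2018, day unknown, and stopped on 12 May. Section 11 sets the onset to 15 May, 3 days after the event ended. With a stop-date check, the first-of-month default gives 1 May and the event stays pre-dose.

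**The case against.** A reader might infer that the stop-date rule turns permitted past use into a breach of the 4-week criterion and removes eligible children from the per-protocol set. The documents do not support that as stated. SAP section 11 imputes only where an analysis needs it and flags imputed values in listings. Nothing says that eligibility deviations or per-protocol membership are derived from imputed dates. Eligibility is rechecked on Day 1 before randomisation (Protocol 6.3). Under SAP section 10.1 deviations come from site monitoring and medical review as well as programming, and the list that contains prohibited medication is confirmed by the Data Review Meeting. These points stand. The sentence on confirmation introduces that second list; eligibility violations are in the list above it, so this safeguard is less explicit for them.

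The 4-week breach also depends on the cohort. Appendix II places screening on D1 for C1-C7, so dosing minus 1 falls inside the window. For C8-C9 screening may be up to 7 days before dosing; the imputed date can then fall after screening, where Protocol 6.5.2 applies instead.

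A second objection is that SAP section 14 confines previous medication to the four weeks before dosing, so the exception never reaches older drugs. That does not rescue the rule. Deciding whether a drug lies within four weeks needs the date that is missing, and medical history has no such limit.

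On the start-date rule, medications stopped before dosing are already protected, so the fault is confined to adverse events. Protocol 7.4.1.2 asks for onset dates and times, and Protocol 7.4.1.3 starts reporting at screening, so affected events should be few. The C1-C7 schedule nevertheless still marks adverse events at pre-screening.

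**Conclusion.** The concern holds in limited form. Section 11 discards a recorded stop month and gives a wrong date by its own terms; for stops 3 to 6 months before dosing it does so in every case examined. The direct effect is old use reported as recent in the previous-medication table. A per-protocol exclusion is a risk that depends on deviation programming using imputed dates. The mITT set, on which Protocol 8.5.1 bases the primary analysis, is untouched, because its malaria exclusion concerns treatment after dosing. SAP section 16.1.1 reports per-protocol results alongside it.

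The number of children affected cannot be computed, because the documents give no count of partial dates. For scale only, assume that children were dropped from a 60-child arm with a 75% observed cure rate. The exact 95% interval is 62.1% to 85.3% for 45/60 (23.1 points wide), 61.6% to 85.6% for 42/56 (24.0 points) and 60.4% to 86.4% for 36/48 (26.0 points). Losing 4 to 12 children would thus widen it by about 1 to 3 points. Those losses are assumptions, not estimates.

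For adverse events, the imputed onset can follow the recorded end. Whether such an event counts as treatment-emergent depends on how an onset equal to the dosing time is programmed, which the definition in section 17.1 leaves open.

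**What to change.** - **Stop dates, previous medication and medical history.** If the month is known, impute the earlier of the last day of that month and IMP start minus 1 day. Use IMP start minus 1 day alone only when the month is also missing.
- **Adverse-event start dates.** If the day is missing and the month is the dosing month, use the IMP start date only when the stop date is not before dosing; otherwise use the first day of the month. Leave the existing protection for medications as it is.
- **Deviations and per-protocol membership.** State that both rest on recorded dates, not imputed ones. The cap does not replace this: for a stop one calendar month before dosing, it still puts 92% to 100% of records inside the window.
- **Definitions.** Reconcile the four-week definition of previous medication in SAP section 14 with the 6-month collection in Protocol 7.2.

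The cost is a few lines of SAP text and matching programming before database lock. No additional data are needed.
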